# 1 PROTOCOL SUMMARY

## 1.1 Study Synopsis

Title:	Single Dose Investigator Initiated Pilot Study to Investigate CYTALUX (pafolacianine) for Intraoperative Imaging of Patients with Endometrial Cancer Planned for Surgery
Study Description:	
This is a single center, single dose, open-label investigator-initiated pilot study in adult subjects with a primary diagnosis of endometrial cancer who are being evaluated for surgery.
 
Subjects will receive one dose of CYTALUX™ (pafolacianine) injection intravenously prior to the planned diagnostic laparoscopies. This hour-long infusion will be completed from 1 hour to up to 168 hours (7 days) prior to intraoperative near-infrared (NIR) imaging for the planned surgery. All subjects participating in the study are expected to receive CYTALUX™ (pafolacianine) injection and standard care laparoscopic evaluation of disease. Intraoperative imaging with Cytalux will be performed for assessment of disease detection in patients who are being evaluated to undergo surgery for endometrial cancer. Any tissues removed as part of standard of care will undergo assessment with NIR light imaging prior to and after resection. This will be then compared to gold standard histologic confirmation by pathology.

Objectives:	
Primary Objective
 
To assess the ability of CYTALUX™ (pafolacianine) injection used with near-infrared (NIR) fluorescent imaging for the detection of malignant tissue in subjects undergoing surgical resection for endometrial cancer
 
Secondary Objectives
 
 
1. To assess the safety of CYTALUX in subjects undergoing surgery for endometrial cancer
 
2. To assess folate receptor (alpha and beta expression) in resected specimens
 
 
Exploratory Objectives
 
 
1. To assess the feasibility of using genomic markers to predict utility of CYTALUX with NIR imaging
 
2. To assess the feasibility of CYTALUX to identify sentinel lymph nodes
 

Endpoints:	
Primary Endpoint
 
The primary efficacy endpoint is the sensitivity of CYTALUX with NIR imaging for detection of malignant lesions. Sensitivity is defined as the proportion of fluorescent light positive lesions that are histologically

[figure not shown]
03 Sep 2025

	
confirmed to be cancer relative to the total number of lesions confirmed to be cancer.
 
Sensitivity = (True Positive)/(True Positive + False Negative)
 
Secondary Endpoints
 
 
1. Incidence rates of all adverse events (AEs), adverse device effects (ADEs), and SAEs, from the time of CYTALUX administration through Visit 3
 
2. Sensitivity for cancerous lesions for:             
 
a. FR<math>\alpha</math> positive lesions
 
b. FR<math>\beta</math> positive lesions
 
 
 
 
Exploratory Endpoints
 
 
1. Genomic evaluation of tumor inclusive of, but not limited to:             
 
a. Estrogen receptor/progesterone receptor (ER/PR) status
 
b. HER2 status
 
c. Mismatch repair (MMR) status
 
d. POLE status
 
e. p53 status
 
f. CARIS whole genome sequencing
 
 
 
2. The exploratory endpoint is the detection rate of CYTALUX with NIR imaging for identification of sentinel lymph nodes (SLNs). The detection rate is the proportion of the patients with SLNs detected by CYTALUX and NIR imaging in all enrolled patients.
 

Study Enrollment:	This study plans to enroll 10 subjects.
Study Population:	Adult subjects (>18 years old) undergoing surgery for endometrial cancer
Phase:	Investigator sponsored study (ISS)
Description of Sites/Facilities Enrolling Participants:	Department of Obstetrics and Gynecology Jordan Center for Gynecologic Cancer at Penn Perelman Center for Advanced Medicine [name]

03 Sep 2025

Description of Study Intervention:	CYTALUX™ (PAFOLACIANINE) INJECTION: folate analog ligand conjugated with an indole cyanine green-like dye as a solution in vials containing 1.6 mL at 2 mg/mL. Each subject will be administered a single intravenous dose of not less than 1 hour before and not more than 168 hours (7 days) before initiation of intraoperative NIR fluorescent imaging.  The imaging systems used in this study will be assessed for meeting the criteria for use with CYTALUX™ (PAFOLACIANINE) INJECTION.
Study Duration:	The recruitment period is estimated at 12 months.
Participant Duration:	The maximum duration a subject is in the study is approximately 2 months.

## 1.2 Study Schematic

03 Sep 2025

### 1.3 Schedule of Activities (SoA)

Study Procedure	Screening Visit	Visit 1	Visit 2	Visit 3
	-30 days prior to surgery	-7 days to day of surgery	Day of surgery	4 weeks ±1 week post-surgery
Informed consent	X			
Medical history	X			
Confirmed surgical candidate	X			
Pregnancy test for patients of childbearing potential		X		
Study drug administration		X		
Surgery with associated procedures including intraoperative imaging and sentinel lymph node biopsy			X	
Histopathology assessment of resected tissue*			X	
Collection of genomic marker data**			X	
AE assessments		X	X	X
ADE assessments			X	X

\*Lesions will be resected during the surgery at Visit 2. Histopathology assessment and immunohistochemistry staining will be completed in accordance with local pathology procedures and timeline.

\*\*Genomic marker data obtained prior to surgery will be utilized, if available. If tissue is collected during surgery for genomic testing, the testing will be completed in accordance with institutional procedures and timeline.

## 2 INTRODUCTION

### 2.1 Study Rationale

Intraoperative molecular imaging, specifically with pafolacianine (CYTALUX), has proven to be a valuable real-time adjunctive tool in identifying cancerous lesions for adults undergoing surgery for ovarian and lung malignancies. Marketing authorization for pafolacianine was granted by the FDA (trade name CYTALUX) on November 29, 2021.

Based on clinical evidence and experience from the phase 2 and phase 3 open-label trials for ovarian cancer and literature demonstrating the overexpression of FR, it is possible that CYTALUX could improve the surgeon's ability to comprehensively stage and resect all disease in endometrial cancer, which is important for delivering appropriate adjuvant therapy and improving outcomes for patients. Endometrial cancer is increasing in incidence, especially high-risk tumors. Innovative tools are needed to provide treatment for this patient population.

This study aims to explore the indication of CYTALUX™ (PAFOLACIANINE) for endometrial cancer. This study will evaluate the efficacy of CYTALUX™ (PAFOLACIANINE) binding to endometrial cancers to detect macroscopic cancers during cytoreductive surgery and assess the sensitivity as an intraoperative imaging adjunct.

03 Sep 2025

Over 80% of advanced (stage III or IV) or recurrent endometrial carcinomas express folate receptor (FR), a folate binding protein, making this receptor an ideal target for marking most endometrial cancers ([May 2025, Senol 2015](#)). This also makes FR an ideal target for intraoperative imaging of this cancer, facilitating cytoreduction, and potentially improving outcomes in these patients ([Kalli 2008](#)). Chemotherapy does not appear to affect FR alpha (FR $\alpha$ ) expression in endometrial cancer specimens as examined by immunohistochemistry ([Despierre 2013](#)), so prior treatment is unlikely to affect utility of FR $\alpha$  ligands as imaging agents.

Immunohistochemistry for FR of representative samples of resected tissue will be performed. This is essential to interpret the results of CYTALUX™ (PAFOLACIANINE) binding and intraoperative fluorescence imaging. Since cytoreductive surgeries typically have several specimens with large amounts of tumor, representative samples from pathology proven sites of cancer will be tested for folate expression and will be correlated with intraoperative fluorescence imaging.

Information on genomic markers for patients receiving CYTALUX will be collected and correlated with intraoperative fluorescence imaging to help predict the utility of CYTALUX with NIR imaging.

## 2.2 Background

Endometrial cancer is the fourth most common cancer for women in the United States ([ACS 2025](#)). Incidence has increased by more than 1% per year since the mid-2000s and mortality is increasing as well; from 2013 to 2022 the death rate rose by 1.5% per year. ([ACS 2025](#)).

Based on data from SEER 2015-2021, the overall five-year survival rate is 81.1% and for distant disease it is only 19.4% ([SEER 2025](#)). The standard management of endometrial cancer is surgery. Other treatments such as radiation, chemotherapy, and immunotherapy may be utilized as well. Tumor-specific intraoperative fluorescence imaging may improve staging and debulking efforts real time during surgery.

## 2.3 Overview of Study Drug

On Target has developed pafolacianine, a folate analog ligand conjugated with an indole cyanine green-like dye as a tumor-specific imaging agent. Pafolacianine binds specifically to the high affinity folate receptor (FR) and could be suitable for use as an imaging agent in patients with tumors that overexpress FR. Following intravenous injection of pafolacianine, the agent distributes throughout the body and is rapidly cleared from healthy tissue, while areas with a high concentration of folate receptors, such as several carcinomas, retain the agent. This fluorescence of the malignant tissue can be captured by an imaging system that can be used by the surgeon along with normal perioperative procedures such as palpation and visual observation to decide which tissues to remove during cytoreduction surgery, particularly after neoadjuvant chemotherapy. Clinical data demonstrate that near infrared (NIR) imaging devices that excite at 760 nm to 785 nm and detect emission at 790 nm to 815 nm are suitable for use with CYTALUX.

Pafolacianine will bind to the FR $\alpha$  receptors and enter the cell through endocytosis. Upon exciting the area under NIR in the appropriate range, the lesions will fluoresce, helping the surgeon identify the osteosarcoma cancer, enabling more complete resection, identification and removal of cancerous synchronous lesions, and adequate margins free of the disease. Pafolacianine has been evaluated in

03 Sep 2025

ovarian cancer (Phase 1, Phase 2, and Phase 3), and also in Phase 2 and Phase 3 studies for intraoperative imaging during surgery for cancer in the lung. In these studies, additional cancer or positive cancer margins were identified in 25% to 40% of the subjects.

In studies using a human cervical carcinoma cell line (KB) that overexpresses FR $\alpha$ , pafolacianine demonstrated a high affinity for FR (KD = 10.4 nM), which compared well with the binding affinity of folic acid (KD = 7.4 nM). In contrast, the D-isomer of pafolacianine (OTL0039) exhibited relatively lower affinity for the receptor (KD = 81.8 nM). Pafolacianine competed well with [H]-folic acid for the receptor, indicating that pafolacianine is highly specific for FR $\alpha$ . In studies conducted in nude mice bearing KB xenografts, fluorescence was observed primarily in the tumors 2.5 hours after intravenous (IV) administration of 10 nmol pafolacianine, with weaker fluorescence signal also seen in the kidneys. Similar sequestration of pafolacianine into the cancer cells is expected to occur when administered to subjects with ovarian cancer undergoing cytoreductive surgery, leaving only FR $\alpha$ + cells visible under the appropriate excitation wavelength.

The safety profile of pafolacianine has been characterized in a comprehensive series of non-human pharmacokinetic and toxicology studies. The results of the pafolacianine Phase 1-enabling nonclinical safety program in rats and dogs demonstrated the safe use of pafolacianine as an intraoperative imaging agent. Additionally, a photoactivation study in rats showed no evidence of phototoxicity associated with pafolacianine. The results of the pafolacianine Phase 1-enabling nonclinical safety program in rats and dogs demonstrated the safe use of pafolacianine as an intraoperative imaging agent. Additionally, a photoactivation study in rats showed no evidence of phototoxicity associated with pafolacianine.

On Target Laboratories has completed the following clinical studies:

- Phase 1 ADME C14 An open-label, mass balance study to investigate the absorption, distribution, metabolism and excretion of [C]-OTL0038 after a single intravenous dose to healthy volunteers (OTL-2019-14COTL0038-001)
- Phase 1a Clinical Study of CYTALUX™ (pafolacianine) injection in healthy volunteers, dosed in 23 subjects with a dose range of 0.025 – 0.20 mg/kg ([CHDR1321A](#)).
- Phase 1b Clinical Study of CYTALUX™ (pafolacianine) injection for the intra-operative imaging of folate receptor alpha positive ovarian cancer, dosed in 12 subjects with a dose range of 0.0125 – 0.0500 mg/kg ([CHDR1321-B](#)).
- Phase 2 Ovarian Clinical Study of CYTALUX™ (pafolacianine) injection for the intra-operative imaging of folate receptor alpha positive ovarian cancer, dosed in 44 subjects with a dose of 0.025 mg/kg ([OTL-2016-CYTALUX™ -003](#)).
- Phase 2 Lung Clinical Study of CYTALUX™ (pafolacianine) injection for the intra-operative imaging of folate receptor alpha positive lung cancer, dosed in 100 subjects with a dose of 0.025 mg/kg ([OTL-2016-CYTALUX™ -005](#)).
- Phase 3 Ovarian Clinical Study of CYTALUX™ (pafolacianine) injection for the intra-operative imaging of folate receptor positive ovarian cancer, dosed in 150 subjects with a dose of 0.025 mg/kg ([OTL-2016-CYTALUX™ \(pafolacianine\) injection-006](#))

03 Sep 2025

- A Phase 3, Single dose, Single-Arm, Open-Label Study to Investigate the Safety and Efficacy of CYTALUX™ (pafolacianine) injection for Intraoperative Imaging of Folate Receptor Positive Lung Nodules, dosed in 112 subjects at a dose of 0.025 mg/kg (ELUCIDATE study) ([OTL-2019-CYTALUX™ -007](#)).

## 2.4 Risk/Benefit Assessment

### 2.4.1 Known Potential Risks

The safety of CYTALUX was evaluated in four open label clinical studies, two studies (N = 44 and N = 150) in patients with ovarian cancer and two studies (N = 100 and N = 112) in patients with known or suspected cancer in the lung. A total of 406 patients received 0.025 mg/kg of CYTALUX via intravenous administration. Adverse reactions that occurred in  $\geq 1\%$  of patients were: nausea (13%), vomiting (5%), abdominal pain (2%), flushing (2%), other infusion-related reactions (2%), hypersensitivity (2%), elevation in blood pressure (1%), dyspepsia (1%), and chest discomfort (1%). Adverse reactions occurred during the administration of CYTALUX in 17% of patients. During the administration of PAFOLACIANINE, interruption of the infusion and/or treatment with an anti-histamine may be required in subjects who experience symptoms suggestive of hypersensitivity, followed by an observational period until the symptoms resolve. Anti-nausea (e.g. Zofran) and anti-histamine (e.g. benadryl) are frequently dosed prior to infusion of Pafolacianine in clinical practice to limit side effects. Symptoms to be aware of may include but are not limited to flushing, nausea, vomiting, abdominal pain and pruritis/urticaria. Other risks to subjects may include injection site adverse reactions (infusion and venous blood sampling), such as infection and hematoma. The use of a near-infrared fluorescence camera system during surgery may result in contamination of the sterile field or injury due to disengagement of the imaging device component coming in contact with the patient and/or surgical team. No clinically meaningful changes in vital signs, laboratory parameters, or electrocardiograms have been observed. Adverse events in the prior studies have been attributable to the underlying disease or to surgery (most commonly lymphedema, post-procedural hematoma, or urinary incontinence). Overall, the administered doses of PAFOLACIANINE have been well tolerated. The time spent visualizing the surgical field under NIR is quite short, with no meaningful prolongation of anesthesia. There are no known hazards associated with exposure of tissue to near-infrared light for short periods of time.

### 2.4.2 Known Potential Benefits

The potential benefits of CYTALUX for the imaging of endometrial cancer are:

- Identification of endometrial cancer burden
- Improved staging of the tumor
- Identification of tissues for further evaluation

### 2.4.3 Assessment of Potential Risks and Benefits

The anticipated benefits appear to outweigh the known and potential risks associated with exposure to PAFOLACIANINE.

03 Sep 2025

### 3 OBJECTIVES AND ENDPOINTS

OBJECTIVES	ENDPOINTS
Primary	
To assess the ability of CYTALUX™ (pafolacianine) injection used with near-infrared (NIR) fluorescent imaging for the detection of malignant tissue in subjects undergoing surgical resection for endometrial cancer	
Sensitivity is defined as the proportion of fluorescent light positive lesions that are histologically confirmed to be cancer relative to the total number of lesions confirmed to be cancer.
 
Sensitivity = (True Positive)/(True Positive + False Negative)

Secondary	

 
1. To assess the safety of CYTALUX in subjects undergoing surgery for endometrial cancer
 
2. To assess folate receptor (alpha and beta expression) in resected specimens
 
	
 
1. Incidence rates of all adverse events (AEs), adverse device effects (ADEs), and SAEs, from the time of CYTALUX administration through Visit 3
 
2. Sensitivity for cancerous lesions for: 
 
a. FR<math>\alpha</math> positive lesions
 
b. FR<math>\beta</math> positive lesions
 
 
 

Exploratory	

 
1. To assess the feasibility of using genomic markers to predict utility of CYTALUX with NIR imaging
 
2. To assess the feasibility of CYTALUX to identify sentinel lymph nodes
 
	
 
1. Genomic evaluation of tumor inclusive of, but not limited to: 
 
a. Estrogen receptor/progesterone receptor (ER/PR) status
 
b. HER2 status
 
c. Mismatch repair (MMR) status
 
d. POLE status
 
e. p53 status
 
f. CARIS whole genome sequencing
 
 
 
2. The exploratory endpoint is the detection rate of CYTALUX with NIR imaging for identification of sentinel lymph nodes (SLNs). The detection rate is the proportion of the patients with SLNs detected by CYTALUX and NIR imaging in all enrolled patients.
 

03 Sep 2025

## 4 STUDY DESIGN

### 4.1 Overall Design

The study will include a screening period of up to 30 days prior to planned surgery to accommodate the typical timing of a pre-surgical consultation between patients and their surgeon and thus avoid the need for subjects to present for a screening visit immediately in advance of their planned surgery. Information from procedures completed as part of standard care during this period can be used for purposes of the trial.

#### 4.1.1 Screening

Screening will overlap with the routine/standard pre-operative screening conducted by the hospital where the surgery is scheduled. Consented patients will be evaluated for eligibility prior to any non-screening study related procedures being performed.

#### 4.1.2 Administration of PAFOLACIANINE

A single dose of PAFOLACIANINE will be administered to each subject 1 to 168 hours (7 days) prior to NIR imaging.

#### 4.1.3 Surgical Procedure

All subjects participating in the study are expected to receive CYTALUX™ (pafolacianine) injection and standard care surgical evaluation of disease. Intraoperative imaging will be completed between one and one hundred sixty-eight hours after CYTALUX™ (pafolacianine) infusion is completed. Any tissues removed as part of standard of care will undergo assessment with NIR light imaging prior to and after resection. This will be then compared to gold standard histologic confirmation by pathology.

After the surgical site is visualized, location of the primary tumor and any clinically suspected additional tumors detected under normal light and/or palpation/endoscopic visualization will be recorded photographically or by video as per surgeon's standard clinical practice. Tumors detected under normal light will be indicated by an "o" on the image as well as on the schematic.

Once normal light assessment is completed, the surgical field will be visualized using an NIR imaging system under fluorescence. Any tumor and/or nodules detected using the NIR imaging system will be recorded on the intraoperative schematic using an "X". Those areas that were also identified under normal light, the "X" will be superimposed on the "O" as "⊗". For nodules identified only under fluorescence, they will be recorded only by an "X".

Light source	Notation
Visible light	O
Fluorescent	X
Both	⊗

03 Sep 2025

#### **4.1.4     *Surgical Tissue Processing – Resected Lesions and Lymph Nodes***

Each lesion obtained for evaluation will be sent to local pathology for processing according to their standard practice. An inventory of specimens sent to local pathology labeled as above will be maintained.

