### **6.3 Measures to Minimize Bias – Randomization and Blinding**

This trial will be an open-label study with no randomization or blinding. All subjects will receive the study drug.

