#### 8.1.3 Visit 2: Surgery

*[Purpose: To collect data on the performance of intra-operative molecular imaging]*

1. AEs and ADEs will be recorded during and following surgery.

03 Sep 2025

2. After the surgical site is visualized under normal light and/or palpation, the number and location of suspect lesions detected under normal light will be recorded on the schematic using an “O”.
3. Following the assessment by normal light, subjects will undergo fluorescence imaging of the surgical field. Suspect lesions detected under fluorescence imaging will be marked on the schematic using an “X”.
4. All identified suspect lesions will be marked on the schematic (“O”, “X”, or “⊗” as described in [Section 4.1.3](#)) and excised, at the discretion of the Investigator.
5. Sentinel lymph node biopsy will be performed at the Investigator’s discretion per the standard of care.
6. All excised lesions will be sent to the local laboratory for histopathology and immunohistochemistry staining. A unique identifier will be assigned to each excised lesion and the location of each will be recorded along with the unique identifier. If an organ/large section of tissue (e.g. uterus, omentum) with multiple lesions is excised *in toto*, one grossly positive lesion will be utilized for the purposes of calculating sensitivity and FR expression.
7. Histopathology, folate receptor expression, and genomic testing results will be recorded once data is received per institutional practices and timeline.

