### **8.2.2 Pathology Samples**

All excised lesions will be processed according to local pathology practices. The final pathology results will be recorded in the CRF.

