## 9 STATISTICAL CONSIDERATIONS

### 9.1 Statistical Hypotheses

- Primary Efficacy Endpoint:
  - The primary efficacy endpoint is the sensitivity of CYTALUX with NIR imaging for detection of malignant lesions. Sensitivity is defined as the proportion of fluorescent light positive lesions that are histologically confirmed to be cancer relative to the total number of lesions confirmed to be cancer.  
Sensitivity = (True Positive)/(True Positive + False Negative)
- Secondary Efficacy Endpoints:
  1. Incidence rates of all adverse events (AEs), adverse device effects(ADEs), and SAEs, from the time of CYTALUX administration through Visit 3
  2. Sensitivity for cancerous lesions for:
    - a. FR $\alpha$  positive lesions
    - b. FR $\beta$  positive lesions
- Exploratory Endpoints:
  1. Genomic evaluation of tumor inclusive of, but not limited to:
    - a. Estrogen receptor/progesterone receptor (ER/PR) status
    - b. HER2 status
    - c. Mismatch repair (MMR) status
    - d. POLE status
    - e. p53 status
    - f. CARIS whole genome sequencing
  2. The exploratory endpoint is the detection rate of CYTALUX with NIR imaging for identification of SLNs. The detection rate is the proportion of the patients with SLNs detected by CYTALUX and NIR imaging in all enrolled patients.

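### Sections 4.1.4 and 8.1.3 do not agree on how specimens are labelled, and nothing keeps the fluorescence result from the pathologist who supplies the reference standard

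*Protocol*

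**What the plan says.** The primary endpoint (Protocol Section 9.1) is sensitivity per lesion, TP/(TP+FN), and histology decides which lesions are cancer. Section 4.1.3 has all tissue removed as standard of care imaged under NIR light before and after resection, and then: "This will be then compared to gold standard histologic confirmation by pathology".

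Section 4.1.3 also defines the light code: O for visible light, X for fluorescence, ⊗ for both. On where it is written, the section says of the first symbol: "Tumors detected under normal light will be indicated by an 'o' on the image as well as on the schematic". The X goes on the intraoperative schematic.

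Section 4.1.4, which follows directly and whose title covers resected lesions and lymph nodes, says: "An inventory of specimens sent to local pathology labeled as above will be maintained". It does not say what the label contains.

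Section 8.1.3 step 6 gives another scheme: "A unique identifier will be assigned to each excised lesion and the location of each will be recorded along with the unique identifier".

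On masking, Section 6.3 says: "This trial will be an open-label study with no randomization or blinding". On pathology, Section 8.2.2 says: "All excised lesions will be processed according to local pathology practices".

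**The concern.** In a diagnostic accuracy study the reference standard should be read without knowledge of the index test. Here the back-reference in Section 4.1.4 can only point to the light code, because no other marking scheme appears before it. That code says whether the tissue fluoresced.

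A pathologist who knows that a specimen fluoresced may take more blocks or levels from it, or lean towards calling an equivocal focus malignant. Both push sensitivity up. Closer sampling of fluorescent tissue finds small cancers there that would be missed in non-fluorescent tissue, and a cancer missed in non-fluorescent tissue is a false negative that drops out of the denominator. A false cancer call in fluorescent tissue adds one to both numerator and denominator.

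The secondary sensitivities in FRα-positive and FRβ-positive lesions rest on the same histology. No later analysis can undo an unmasked read, so the point has to be settled before the first operation.

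**Working it through.** **1. The text side by side**

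| Question | Section 4.1.3 / 4.1.4 | Section 8.1.3 step 6 |
|---|---|---|
| What identifies a specimen? | Refers back to earlier labelling; only O/X/⊗ is defined | Unique identifier plus location |
| Where is the light code written? | Image and schematic | Schematic (steps 2 to 4) |
| Does pathology receive the light code? | Not stated | Not stated |
| Is it withheld from pathology? | Not stated | Not stated |

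The two sections give different labels. Neither they nor Sections 6.3 and 8.2.2 protect the reference read.

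**2. Direction and size of a possible bias**

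The protocol states no expected sensitivity, lesion count or power, so there is no figure of its own to reproduce. All values of s, d1, d0 and r below are assumptions.

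Let s be the true sensitivity, and let d1 and d0 be the probabilities that histology finds a cancer that is present in a fluorescent and in a non-fluorescent specimen. Then

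observed sensitivity = s·d1 / (s·d1 + (1 − s)·d0) = s / (s + (1 − s)·r), with r = d0/d1.

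With a masked read r = 1, and the expression returns s. With r below 1 it exceeds s:

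- s = 0.50, r = 0.9: 0.50 / (0.50 + 0.45) = 0.526
- s = 0.50, r = 0.8: 0.50 / (0.50 + 0.40) = 0.556
- s = 0.70, r = 0.9: 0.70 / (0.70 + 0.27) = 0.722
- s = 0.70, r = 0.8: 0.70 / (0.70 + 0.24) = 0.745

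False cancer calls act in the same direction. With 10 true cancers of which 5 fluoresce, one benign fluorescent specimen called cancer moves 5/10 = 0.500 to 6/11 = 0.545.

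**3. Effect on the stated test**

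Section 9.2.2 sets an exact binomial test, two-sided alpha 0.05, against 0.10. Assume 10 independent lesions; the protocol gives 10 subjects but no lesion number. The test then rejects upward at 4 or more positives, with probability 0.0128 when the true sensitivity is 0.10.

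- r = 0.9: 0.10 reads as 0.10 / (0.10 + 0.81) = 0.110, and the chance of 4 or more of 10 is 0.018
- r = 0.8: 0.10 reads as 0.10 / (0.10 + 0.72) = 0.122, and the chance is 0.025

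In this range the test moves little. The estimate moves by about 2 to 6 percentage points at s = 0.50 to 0.70.

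**The case against.** A reader might infer that the pathologist will read every specimen with the fluorescence result in hand. The protocol does not say so. Section 4.1.3 puts the code on the image and schematic, never on a container or requisition. The back-reference in Section 4.1.4 may describe a study-side inventory rather than the specimen label. The identifier in Section 8.1.3 step 6 may be what specimens actually travel under. In a single-arm study the no-blinding statement in Section 6.3 is most naturally about treatment. All of this stands, so exposure of the pathologist is a possibility that the text leaves open, not a stated procedure.

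A reader might also infer a large bias. An assumed r of 0.5 would turn 50% into 0.50 / (0.50 + 0.25) = 67%, but nothing in the protocol supports a value that low. Section 2.1 is aimed at macroscopic cancer, and under Section 8.1.3 step 6 an organ or large section with several lesions contributes one grossly positive lesion. Such a lesion is not missed for want of an extra block.

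What does not fall away is the lack of protection. On the lenient reading Section 4.1.4 points to a label that it never defines, and pathology is left to local practice with no instruction to withhold the light code. Open-label dosing does not require an unmasked reference read.

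**Conclusion.** The point holds as an unreconciled label and an unprotected reference read. If knowledge of fluorescence has any effect on sampling or calls, the expected effect on sensitivity is upward. Its size cannot be taken from the protocol: the shifts to 53% to 56% and to 72% to 74% rest wholly on the assumed r of 0.9 to 0.8. The risk lies mainly with lymph nodes and grossly normal tissue. It concerns the sensitivity estimate and its confidence interval, which are what a 10-subject pilot has to offer, more than rejection of 0.10. It is worth correcting because the correction is cheap and cannot be made after the specimens have been read.

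**What to change.** - **Section 4.1.4:** replace the back-reference so that it agrees with Section 8.1.3 step 6. Specimens go to local pathology under the unique identifier and anatomical site only. The O/X/⊗ code stays on the schematic and in the study inventory and is linked to histology by identifier after the final report is issued.
- **Section 6.3:** add that histology and folate receptor immunohistochemistry are read without knowledge of the fluorescence result.

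The cost is about one sentence in each section, a change to the specimen label, and a simple linking step using an identifier that the protocol already assigns. The downside is that the surgeon can no longer use the light code on the requisition to steer sampling; site and clinical description remain available.
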